3. POTENTIAL BENEFITS OF THE PROPOSED RESEARCH TO THE SUBJECTS AND OTHERS

We hope that the emotion regulation training of the iTRAC intervention will be successful in reducing the rates of sexual onset and other health risks in our subject population. Waitlist control participants will be provided the opportunity to complete iTRAC-SRP after a 6-month delay. We believe that the clear examination of these questions outweighs the previously mentioned risks. Youth have an opportunity to learn emotion regulation strategies and consider safer sexual behavior to avoid future risks. The potential benefits to individual subjects outweigh potential risks, particularly in offering adolescents a chance to better understand the nature and consequences of their risk behaviors and to learn skills related to emotion regulation.

4. IMPORTANCE OF THE KNOWLEDGE TO BE GAINED

This study will provide an important sex education tool and elucidate the role of emotion regulation in improving sexual self-efficacy, a critical factor in healthy sexual activity during development, and delaying early sexual debut, which is associated with significantly greater future sexual risk, including more unwanted pregnancies, more sexually transmitted infections, greater number of sexual partners, greater frequency of intercourse, and less condom use. Even if an adolescent or parent does not directly benefit from the project, the information we gain may be used to improve the effectiveness of sexual health programs for other early adolescents.

5. HUMAN SUBJECTS PROTECTION EDUCATION

To meet mandatory training certification in Human Subjects Protection, the Office of Research Administration offers an online training program through CITI, Collaborative IRB Training Initiative. This online program offers both the initial certificate and a three-year re-certification program required by Lifespan. Drs. [name], [name], and [name] have completed required training through CITI.

Klein Buendel, Inc. maintains compliance with mandatory training through the NIH Office of Extramural Research's training program. [name] and all required staff members have completed this training.

Collaborating Sites

This research involving human subjects will take place at both Rhode Island Hospital (FWA#00001230) and the participating school districts. School sites will be made aware by project staff of proper procedures for reporting any issues related to risks related to human subjects. Due to their limited role in the study (informing families about the availability of research and permitting use of their facilities for intervention) schools do not meet criteria for engagement in research according to OHRP guidance (dated October 16, 2008). Rhode Island Hospital will provide the oversight review board for the study for all activities occurring in Rhode Island. Western Institutional Review Board will provide oversight for any study activities taking place at Klein Buendel (FWA#00003715).

DATA AND SAFETY MONITORING PLAN

The nature of the population and setting warrants the development of a Data Safety and Monitoring Plan. The current study is considered to present minimal risk to participants given that subjects will provide data via questionnaires and performance measures as well as participate in a psychosocial intervention. In this plan, the Principal Investigator with input from colleagues ([name], [name], [name]) will provide oversight of all recruitment and study procedures.

Specifically, the Principal Investigator will take primary responsibility for:

- Monitoring the safety of the participants

It is possible, though it has never happened, that adolescents in the schools may become aggressive with each other. Each school has identified personnel who are present during after school activities, and session moderators will have cell phones to contact any necessary assistance.

- Monitoring the safety of the researchers

It is possible, though unlikely, that the physical safety of the PI and facilitators could be threatened, either through direct implementation of the study (e.g., a participant becomes agitated and assaults a facilitator) or while in the school environment more generally (e.g., an adolescent uninvolved in the study assaults a facilitator at the school for the project). To help prevent and/or respond to such occurrences, school staff will be on-site for assistance. Such events are unlikely to occur, but in the case that they do, the event will be reported to the PI and school staff immediately. If any project staff is injured as a result of such an event, they will seek care, as warranted, by Rhode Island Hospital's Employee Health Services.

Home visits will be conducted in pairs, to ensure staff safety. Lab procedures include providing supervisors with time and location of all home appointments and texting a supervisor prior to entering the home as well as when the pair has left.

- Maintaining the confidentiality and integrity of the data

Data will be confidentially maintained under the stringent guidelines put forth in the aforementioned **Protection Against Risk** (see **Human Subjects Protection**). RIH will maintain locked files, stored off-site, and permit electronic access only to authorized individuals. ID numbers are used as identifiers throughout databases. The collaborating schools and any associated staff members will under no circumstances have any access to records.

- Receiving/eliciting reports of adverse events from research assistants (RAs) and school staff

The PI will receive these reports on an event-by-event basis. They will also be elicited in an open-ended manner through regular contact between the PI and school staff.

- Reporting adverse events to:

Co-investigators

School

The Rhode Island Hospital IRB

The Program Officer at NIH

The major adverse event that could occur as a result of study participation includes psychological distress from study procedures resulting in hospitalization. Project staff will be instructed to immediately contact the PIs when they first become aware of any event that could potentially be considered adverse. The PIs will immediately investigate the event and determine the appropriate manner in which to proceed. It is the responsibility of the PI to review serious adverse event reports, provide commentary, and provide oversight to ensure that reports are relayed to the co-investigators, Rhode Island Hospital IRB, and to the OHRP, as indicated. In the event of adverse events or unexpected problems posing risks to subjects, the PI is empowered to modify protocols and/or request interim data analyses.

Department of Health and Human Services (DHHS) Required Education in the Protection of Human Research Participants

To meet mandatory training certification in Human Subjects Protection, the Office of Research Administration offers an online training program through CITI, Collaborative IRB Training Initiative. This online program offers both the initial certificate and a three-year re-certification program required by Lifespan. Drs. [name], [name], [name], and all research staff in their laboratory have completed required training. Klein Buendel, Inc. maintains compliance with mandatory training through the NIH Office of Extramural Research's training program. [name] and all required staff members have completed this training.

REFERENCES

2. CDC. Youth risk behavior surveillance-United States, 2017. *Morbidity and Mortality Weekly Report*. 2017;
3. National Research Council. *Adolescent health services: missing opportunities*. Washington, DC: The National Academies Press; 2009.

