Treatment Mechanisms (Mediators): *Emotion regulation* will be measured via self-report, performance measures, and parent observation. Teacher measures were considered; our experience in Project TRAC was that students changed teachers too frequently for long-term follow-ups and that short-term follow-ups (2 months) did not provide time for the ER skills learned for risk situations to generalize to non-risk settings, like the classroom⁴⁸. **Self-report:** The Difficulties in Emotion Regulation Scale (36 items¹²⁰) uses six subscales (e.g., lack of emotional awareness, limited access to ER strategies; all $\alpha \geq .80$) to assess perceptions of skill in ER based on Linehan's theoretical work.¹²¹ The Affect Dysregulation Scale (6 items¹²²) assesses the frequency of difficulties with ER ($\alpha = .72$), and is shown to be related to adolescent risk behaviors.¹²² The Emotion Regulation Behaviors Scale- Revised (9 items¹²³) measures use of the specific emotion regulation strategies taught in iTRAC ($\alpha = .73$). The emotional self-efficacy subscale of the Self-Efficacy Questionnaire for Children (8 items¹²⁴) assesses perception of one's ability to cope with negative emotions ($\alpha = .83$). It has been shown to be valid, reliable, and related to risk behaviors among adolescents.¹²⁴ The Implicit Theories of Emotions for Children- Self subscale (6 items)¹²⁵ is based on Dweck and colleagues' work on implicit theories of intelligence¹²⁶ and Tamir's adult measure of emotion malleability. ENREF 146¹²⁷ It assesses adolescents' beliefs about the controllability of their emotions ($\alpha = .86$). All of these measures were successfully used in the iTRAC study. **Performance measures:** a) Diagnostic Analysis of Nonverbal Accuracy-2⁵⁰ (DANVA2) is a computer-based measure that asks participants to identify the emotion of facial expressions displayed in photographs. The measure has shown one-month test-retest reliability over .8⁵⁰ and had an alpha of .83 in Project TRAC. b) Behavioral Indicator of Resiliency to Distress (BIRD)¹²⁸ is a 5-minute computerized distress tolerance task in which participants are given the option to quit at any time. It generates a score of time spent persisting on a frustrating task that provides negative feedback (aversive noise) when users fail at the task.¹²⁸⁻¹³⁰ **Parent report:** The Adolescent Self-Regulatory Inventory (29 items)¹³¹ measures perceptions of adolescents' abilities to regulate over the short-term and long-term, separately; both adolescents and parents will complete it about the adolescent ($\alpha = .75-.90$). Parents will complete this measure at baseline and 6-months, to reduce burden.

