Once permission to contact the family has been received, school staff involvement ends (to avoid perceived pressure to participate). Trained research staff will contact parents to arrange an individual meeting to describe the project activities they are being asked to complete and obtain parental consent. Participants will be compensated for their time and effort. Staff will separately explain the project to adolescents and obtain assent away from their parent's presence.

These procedures will be used for both Phase 1 and Phase 2. Fewer homerooms will need to be approached for the Translation and Acceptability stages, as fewer participants are needed.

A Health Education Professionals Panel of school personnel key to student health will also be formed to advise on the adaptation of the intervention to digital format. Identified from throughout the school system, this will include individuals with involvement in student health and risk behaviors (e.g., health teachers, administrators, school counselors, school nurses). Once each pool of professionals from Cranston Public Schools is identified, individuals within each profession will be chosen at random, to ensure a mix of perspectives are represented in the HEPP. They will be contacted using their publicly available school email addresses and offered participation. Additionally, members of the Rhode Island Department of Health (RIDOH) school nurses listserv, as well

as representatives from the Planned Parenthood Federation of America, will be contacted and encouraged to outreach study staff if interested in participating.

Adolescent participation for all activities will require parent consent and adolescent assent. Adolescents and their parents will be agreeing to let us use adolescent feedback as data for program adaptation and development in the Translation and Acceptability Testing stages. In the RCT stage, adolescents and their parents will be agreeing to the adolescent's participation in an 8-module tablet-delivered health intervention and completion of computerized questionnaires at three points (baseline, 2-, and 6-month follow-ups). Similarly, parents will provide responses to questionnaires. They will be agreeing to let their responses, collapsed with those of other participants, be used for reporting scientific results. Adolescents and their parents will be assured that they are free to withdraw from the study at any time.

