Participants in the Randomized Trial (Phase 2) will complete audio computer-assisted self-interviews (ACASI) on laptops at baseline, 2-, and 6-months after baseline. Adolescents will complete several questionnaires assessing demographic information, sexual attitudes and cognitions, risk behaviors, and emotional functioning. Parents will complete a locator form to assist in retention and tracking, as well as measures of demographic information and their adolescent's emotion regulation. Teens will also complete performance measures related to emotion regulation (Behavioral Indicator of Resilience to Distress; Diagnostic Analysis of Nonverbal Accuracy-2).

c. Potential Risks

The risks in this study are considered minimal. During the Translation phase, participation requires only attendance at Advisory Board meetings where opinions will be shared, though participants will be advised that they may decline to answer any questions at any time. During Acceptability Testing, participation requires completion of the web-based program across several sessions, and completion of measures and interviews that assess the acceptability and clarity of the web-based program. Similarly, during the RCT, participation requires completion of measures as described above and participation in the finalized web-based program.

Some adolescents and parents may feel uncomfortable with the topics regarding sexual health. Families are notified of this content during the informed consent process. These topics will be discussed sensitively and openly, in a developmentally appropriate way during all phases of the project. Moderators during feedback

sessions will be trained to help participants with topics of sex and sexuality. In addition, they will heavily encourage confidentiality and respect.

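### Adverse events are collected passively, from research assistants and school staff only; no visible text provides for asking adolescents or parents, and in the Phase 2 RCT volunteered events would surface unequally by arm

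*Combined protocol and SAP*

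**What the plan says.** The Data and Safety Monitoring Plan lists among the Principal Investigator's duties "Receiving/eliciting reports of adverse events from research assistants (RAs) and school staff". Reports arrive event by event. The only active enquiry described is with schools: "They will also be elicited in an open-ended manner through regular contact between the PI and school staff". For the study team the trigger is awareness: "Project staff will be instructed to immediately contact the PIs when they first become aware of any event that could potentially be considered adverse".

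The same plan names the event it has in mind: "The major adverse event that could occur as a result of study participation includes psychological distress from study procedures resulting in hospitalization".

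The Sources of Materials section describes what families are asked in the RCT. For teens: "Adolescents will complete several questionnaires assessing demographic information, sexual attitudes and cognitions, risk behaviors, and emotional functioning". Parents complete a locator form "as well as measures of demographic information and their adolescent's emotion regulation". The Measures section lists the instruments, and none is an adverse-event, emergency-care or hospitalization item. On the parent rating of adolescent self-regulation, Measures says "Parents will complete this measure at baseline and 6-months, to reduce burden"; the compensation schedule likewise gives parents two assessments, at baseline and 6 months. The Potential Risks section says that abuse is not directly assessed but is acted on if disclosed, with a similar protocol for suicidal or homicidal ideation.

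**The concern.** The sources do not match the event. A hospitalization for distress would normally happen away from school and away from study visits. Parents would know of it; a research assistant or teacher would know only if told. Nothing in the visible text prompts anyone in the family to tell them. The study visits do not clearly fill the gap, because the computerized interview is chosen so that others do not see the answers, and the Columbia Impairment Scale serves only as a moderator and is not tied to safety reporting.

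Two things are at stake. First, the investigator's authority to modify the protocol or request interim analyses is useful only if events are known in time. Second, in the RCT one arm meets staff repeatedly during the module weeks and the other does not. With passive reporting, equal true risks would yield unequal counts, and a report that no events occurred would carry little weight.

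**Working it through.** The documents give no adverse-event rate and no disclosure rate, so there is no stated figure to reproduce. The contact counts below come from the documents; the detection figures are illustrations.

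**Scheduled questions about events.** Adolescents: 0 at 2 months, 0 at 6 months. Parents: 0. This is the same in both arms.

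**Scheduled staff contacts after baseline.**
- Both arms: assessments at 2 and 6 months, so 2 contacts (Assessment Procedures; Waitlist Control Condition).
- iTRAC-SRP only: eight supervised modules at one or two a week over 4 to 8 weeks (Intervention Condition). That is 8 visits, or 4 if two modules share a visit (an assumption).
- Totals: 8 + 2 = 10, or 4 + 2 = 6, against 2. The ratio is 3 to 5.
- From month 2 to month 6 each arm has one remaining contact, about 4 months away for an event just after month 2. All the excess lies in the module weeks.

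**Illustration of unequal capture.** Let c be the chance that an event is volunteered at any one later contact, and k the number of contacts still to come. The chance that it surfaces is 1 − (1 − c)^k. Take c = 0.20, equal true risk, and events spread evenly over 6 months, so one third fall in months 0–2 and two thirds in months 2–6.

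1. Months 2–6: k = 1 in both arms, giving 20% and 20%.
2. Months 0–2, waitlist: k = 2, giving 1 − 0.8² = 36%.
3. Months 0–2, iTRAC-SRP, one module at the end of each of 8 weeks: k runs from 10 down to 3. The average of 0.8^k over those eight values is 0.266, giving 73%.
4. Overall, iTRAC-SRP: (1/3)(73%) + (2/3)(20%) ≈ 38%. Waitlist: (1/3)(36%) + (2/3)(20%) ≈ 25%.

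**Sensitivity, same method.** The 4-week column assumes one visit a week with two modules each. For it, k runs from 6 down to 3 in weeks 1–4 and is 2 in weeks 5–8.

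| c | iTRAC-SRP, 8 weeks | iTRAC-SRP, 4 weeks | Waitlist |
|---|---|---|---|
| 0.05 | 13% | 8% | 7% |
| 0.10 | 23% | 16% | 13% |
| 0.20 | 38% | 30% | 25% |
| 0.30 | 49% | 42% | 37% |

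The direction is the same throughout. The size ranges from small to nearly twofold (12.6% / 6.6% = 1.9 at c = 0.05 over 8 weeks).

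**What a count of zero would mean.** Assume 60 per arm (the allocation ratio is not stated) and a true risk of 2%. The chance of recording no event in an arm is (1 − 0.02)^60 = 0.30 with full capture and (1 − 0.02 × 0.5)^60 = 0.55 if half of events surface.

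**The case against.** The strongest reply is that this is a minimal-risk study with more eyes on participants than the duty list suggests. Each school has a dedicated research assistant who stays with the family, staff are at each school at least three days a week, and volunteered disclosures are acted on. Consent pages were removed and may tell families how to report problems. The submission seeks approval for Phase 1 only, which has no arms and no program exposure. All of this stands. It means events can be missed or learned late, not that they will be, and that the two waitlist contacts are those scheduled, not a ceiling. But these are opportunities for someone to volunteer an event; none is a question.

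A reader might infer more than the documents support:

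- *That schools drop out as a source.* The sentence ending school staff involvement once contact is permitted concerns recruitment pressure. Afterwards schools are told how to report risk issues, personnel are present after school, and the investigator keeps regular contact with them.
- *That parents are not contacted until month 6.* Locator forms, with a parent signature procedure, are completed at each assessment point, and session reminders go to parents. What is absent is a parent assessment, and an event question on the form.
- *That detection would be 89% against 36%.* That is 1 − 0.8^10 against 1 − 0.8², which requires the event to precede every contact. Events from month 2 onward have equal scheduled follow-up in both arms.
- *That a planned by-arm event analysis is biased.* The Statistical Design and Power section plans no such comparison. The issue arises only if arms are described side by side.

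**Conclusion.** The gap is real: no scheduled event question to adolescents or parents in either arm, for a named event that families would usually learn of first. Unequal observation is also real but bounded: 6 to 10 scheduled contacts against 2, confined to the first 4 to 8 weeks of the Phase 2 RCT. At an assumed 20% disclosure per contact, events even over 6 months and weekly modules, about 38% against 25% would surface; for events in the first two months it is 73% against 36%. The disclosure rate, event timing and visit pattern are all assumptions.

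The documents do not support saying that families are barred from reporting, that harm would certainly go unseen, or that the remark that TRAC sexual health content ran without adverse events in a previous trial is wrong; how that trial monitored events is not shown. This is a worthwhile, low-cost improvement to settle before Phase 2, not a defect in the efficacy analysis.

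**What to change.** Add the same two or three fixed items to the adolescent 2- and 6-month batteries and the parent 6-month battery in both arms: any emergency or inpatient care, and any marked upset linked to study activities, since the last assessment. A short parent version can accompany the 2-month locator form. State who reviews positive answers and how promptly, because self-administered responses may otherwise sit unread, and make sure the consent and assent text says these answers will be read.

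Add one sentence to the monitoring plan: any description of events by arm rests on the scheduled items, and events volunteered to research assistants or school staff are listed separately. Scheduled adolescent questions then number 2 against 2.

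The cost is a few REDCap items, about a minute of burden, and more minor events to review. Adding a prompt to existing parent reminder texts is not an equivalent shortcut. Those texts concern intervention sessions, which waitlist families do not have during the 6 months, so matched prompts would need a new message stream.

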144. Office of Disease Prevention and Health Promotion. *Healthy People 2030*. <https://health.gov/healthypeople/objectives-and-data/data-sources-and-methods/data-sources/national-survey-family-growth-nsfg>

STATISTICAL DESIGN AND POWER

Data preparation: Relevant tests of model assumptions will be evaluated with all analyses, and appropriate corrections for problems in distributions will be implemented. Because even small and statistically non-significant between condition differences in baseline characteristics can adversely affect treatment effect estimates, we will use inverse probability of treatment weights (IPTW) to adjust for potential imbalance between conditions^{1,2}. Covariate balancing propensity scores³ will be used to generate the weights and the model will include demographics and baseline measures of primary outcomes, secondary outcomes, exploratory outcomes, moderators, and mechanisms. The effectiveness of the IPTWs will be evaluated by looking at the average and largest effect sizes for between condition differences prior-to and following weighting. We will also examine the positivity or common support assumption required for IPTW by visually examining the overlap in propensity score distributions for each condition. This assumption is likely to hold in the context of a randomized trial.

Missing data: Based on previous projects, we expect 10% attrition by the end of the 6-month follow-up. We will use fully conditional multiple imputation (a.k.a., multiple imputation using chained equations [MICE]⁴) to address bias introduced by missing data. MICE was selected because it can handle outcomes with different statistical distributions (i.e., binomial, Poisson, normal), it can be applied to a large number of variables, and it has solid performance in simulation studies⁴. This approach assumes data are missing at random (MAR).

Primary Outcome: The primary outcome of the RCT will be Self-efficacy for Sexual Risk Prevention at the 6-month follow-up. All participants who were randomized will be included in all analyses (i.e., intent-to-treat). This outcome will be assessed using an analysis of covariance with baseline included as a covariate.

Secondary Outcomes: Secondary outcomes include sexual health knowledge, abstinence attitudes, sexual behaviors, and condomless sex acts. Sexual health knowledge will be analyzed like the primary outcome. Sexual behaviors will be summed across the follow-up assessments. Multiple imputation will be used to address missing assessments and the summation will occur within each imputation to ensure that missing assessment are appropriately counted. These data are expected to be zero-altered and will thus be analyzed using generalized linear models with a negative binomial distribution and a log link function. Condomless sex acts will be analyzed like sexual behaviors.

Mechanisms: Measures of mechanisms include theoretically important emotional competencies (e.g., emotion regulation, emotion recognition, distress tolerance) that mediate risk as measured by self-report, performance measures, and parent report. These outcomes will be assessed at the 2-month and 6-month follow-ups using analysis of covariance like for the primary outcome.

Power and Sample Size: This trial was powered to the continuously scaled outcomes (self-efficacy, knowledge, and emotional competencies). With 120 participants, this study is powered at .80 to detect moderate effect sizes (standardized mean difference $d \geq .47$). The power analysis was run using the R package simstudy v0.2.1 and assumed a two tailed type-1 error rate of .05 and a correlation between baseline and the 6-month outcome of $r=.6$. Effect sizes from our previous work showed effect sizes ranging from .20 to .70.

Exploratory analyses of mediation and treatment modifiers: **Mediation:** Causal mediation will be used to evaluate whether treatment-related change in self-efficacy was attributable to change in mechanisms. Causal mediation was selected because the framework can handle mediators and outcomes with non-normal distributions such as a binary outcome⁸. Mediation analyses will be run for each of the hypothesized mechanisms. **Moderation:** To better understand who is benefiting most from the intervention we will use causal random forests, a non-parametric data-mining procedure⁹. Although this principled exploratory approach cannot definitively define subgroups, it has better statistical properties than looking at individual moderators and will help suggest subgroups that differ in terms of their response to the intervention. Power was not calculated for these exploratory analyses.

